1.2. Study Design

Overview of Study Design and Key Features	

The diagram illustrates the study timeline. It begins with a 'Pre-screening Period (0-4 weeks)' followed by a 'Run-in Week -4 to -1'. The main study period starts at 'Visit 0' (Week 0) and continues until 'Visit 15-2' (Week 56). 'PK Sampling' is indicated at various points. The study is divided into two parallel treatment arms: 'SOC***+ Mepolizumab 100mg' and 'SOC***+ Placebo'. Both arms include 'Standard of care asthma therapy'. Randomization (R*) occurs at Visit 0. An 'Exit Visit' is marked at Visit 15-2. A note specifies that PK sampling is for a sub-study only.
	
Design Features	
 This is a bridging study. Multi-centre, randomized, placebo-controlled, double-blind, parallel-group design. In the main study, there will be a total of 16 clinic visits conducted on an outpatient basis. Subjects who discontinue study treatment will not be automatically withdrawn, but will be encouraged to stay in the study and complete all remaining protocol specified visits and be followed-up as per the protocol until the completion of the follow-up assessments. The total duration of subject participation in the main study, including run-in will be 53 to 56 weeks. Subjects will remain on their current maintenance therapy throughout the run-in and double-blind treatment administration periods.
Study intervention	
 Subjects will be randomized on Day 1 to receive mepolizumab (100 mg) SC or placebo SC added onto their existing therapy for asthma every 4 weeks for a total of 13 doses
Study intervention Assignment	
 Randomization to study treatment will be stratified by blood eosinophil count at screening (≥ 300 cells/μL and < 300 cells/μL). Subjects will be randomized in a 1:1 ratio to receive either mepolizumab SC or placebo SC.
Interim Analysis	
 No formal interim analysis is planned

Overview of Study Design and Key Features

	
• Blinded evaluation of exacerbation rates is planned for this study. This will be done under blinded situation and will not treated as formal interim analysis.
--	--

2. STATISTICAL HYPOTHESES

This is a bridging study designed to determine the effect of Mepolizumab 100mg SC on clinically significant exacerbation events, compared with placebo among Chinese subjects.

The Chinese patient data collected in this study will be supplemented with data on the treatment effect for the same exacerbation endpoint from the global PhIII study MEA115588, using a Bayesian Dynamic Borrowing approach to analysis of the study ([Schmidli, 2014](#)). The potential to borrow information from the global dataset is based on the premise that the underlying disease, its general management and the response to mepolizumab is similar in Chinese and non-Chinese patients. A bridging approach is proposed because of the expected similarity of the treatment effect in Chinese patients and the global population (supported by similarities in the epidemiology, pathophysiology, pharmacology and clinical management of patients and consistency of treatment differences across key demographic factors including ethnicity), and similar study design specially the study population (supported by similarities in key eligibility criteria) between MEA115588 and this China study, hence there is low probability of the null effect being true.

A frequentist hypothesis test will not be performed. Instead, the posterior distributions of the primary endpoint, i.e. rate ratio of events between Mepolizumab 100mg SC vs. placebo will be derived based on the Bayesian analysis including the global PhIII study MEA115588 information and the data collected on Chinese patients in this study. The hypothesis of interest for treatment comparison is that the rate ratio is less than 1, and the study will be considered to have shown evidence that supports this hypothesis if the posterior probability that the rate ratio is less than 1 is at least 95% (a “positive result”).

There is no adjustment for multiplicity in this study.

3. ANALYSIS SETS

Analysis Set	Definition / Criteria	Analyses Evaluated
All Subjects Enrolled (ASE)	All subjects enrolled and for whom a record exists on the study database	Summarizing reasons for screen and run-in failures
Modified Intent-to-Treat (MITT)	All randomized subjects who receive at least one dose of trial medication	The primary population for all analyses of efficacy and safety data
Per Protocol (PP)	All subjects in the Modified Intent-to-Treat population not identified as full protocol deviators with respect to criteria that are considered to impact the primary efficacy analysis.	Supplementary analysis of the primary endpoint
Pharmacokinetic (PK)	All subjects in the PK sub study* who received at least one dose of study medication and for whom at least one pharmacokinetic sample was obtained, and analyzed.	Primary population for assessing PK

* The subjects in the PK sub study means the subjects who signed ICF of PK sub study. One subject (ID: PPD [REDACTED]) signed ICF for PK sub-study but withdraw the ICF for PK sub-study at Visit 2 since the number of subjects for PK sub study was full, therefore this subject will not be included in PK population.

4. STATISTICAL ANALYSES

4.1. General Considerations

Since this is a bridging study, the results from MEA115588 will be borrowed and compared with the data from this study. To ensure comparability between two studies, the Estimand framework including analysis models will be similar with MEA115588 unless otherwise specified.

4.1.1. General Methodology

In the case of wrong stratification assigned at the time of randomization, the analyses will be performed based on the actual stratum per data collected in the CRF.

Confidence intervals will use 95% confidence levels unless otherwise specified.

Unless otherwise specified, the following will apply:

- Continuous data will be summarized using descriptive statistics: n, mean, standard deviation (std), median, minimum, 25th percentile, 75th percentile and maximum.
- Categorical data will be summarized as the number and percentage of participants in each category.
- The minimum and maximum will be reported to the same number of decimal places as the raw data recorded in the database. The mean, median, 25th percentile, and 75th percentile will be reported to one more decimal place than the raw data recorded in the database. The SD will be reported to two more decimal places than the raw data recorded in the database. A maximum of four decimal places will be used. Percentages will be presented to one decimal place. A count of zero will have no corresponding percentage.
- When the data are summarized by visit, only scheduled visits will be presented.

4.1.2. Baseline Definition

For all endpoints (except as noted in baseline definitions) the baseline value will be the latest pre-dose assessment with a non-missing value, including those from unscheduled visits. If time is not collected, Day 1 assessments are assumed to be taken prior to first dose and used as baseline.

For data collected via the eDiary device (i.e. morning peak flow, usage of rescue medication (i.e. salbutamol/albuterol), asthma symptom score and frequency of awakening due to asthma symptoms), the baseline for analyses of averaged 4-weekly data will be calculated using values from the run-in period as shown in Section 4.2 in protocol.

Parameter	Study Assessments can be Considered as Baseline			Baseline Used in Data Display
	Screening	Day -6 to Day 1	Day 1 (Pre-Dose)	
[Efficacy]				
Salbutamol/albuterol use		X		Average of measurements from Day -6 to Day 1 pre-dose
Asthma symptom scores		X		Average of measurements from Day -6 to Day 1 pre-dose
Awakening at night		X		Average of measurements from Day -6 to Day 1 pre-dose
Morning PEF		X		Average of measurements from Day -6 to Day 1 pre-dose
[Safety]				
12-Lead ECG	X			Screening

Unless otherwise stated, if baseline data is missing no derivation will be performed and baseline will be set to missing.

4.1.3. Definition of endpoint(s)/estimands

The primary endpoint is the frequency of clinically significant exacerbations (the same as protocol defined exacerbations) of asthma over the 52 weeks treatment period expressed as an exacerbation rate p.a.

Exacerbation from the start of treatment until 4 weeks after the last dose of study drug will be used in the analysis. Exacerbations which are separated by less than 7 days will be treated as a continuation of the same exacerbation.

The estimand is described by the following attributes:

- Population: Chinese participants with severe eosinophilic asthma.
- Treatment condition: mepolizumab 100mg SC given every 4 weeks compared to placebo every 4 weeks, both treatments given on top of standard of care. Further details on standard of care can be found in Section 6 of Protocol.
- Variable: number of clinically significant exacerbations over 52 weeks.
- Summary measure: annualised rate of exacerbations. Comparison between the mepolizumab arm and placebo will be assessed with the rate ratio.
- Intercurrent events:
 - Study treatment discontinuation-hypothetical strategy
- Rationale for estimand:

Interest lies in the treatment effect when medication is taken as directed. For participants discontinuing randomised medication, use of a hypothetical strategy addresses treatment effects attributable to mepolizumab in the hypothetical scenario where participants would not discontinue from treatment.

Since this is a bridging study, the results from MEA115588 will be borrowed and compared with the data from this study. To ensure comparability between two studies, the Estimand framework including analysis models will be similar with MEA115588.

4.2. Primary Endpoint(s) Analyses

4.2.1. Main analytical approach

The primary efficacy analysis will evaluate the primary estimand in the Modified Intent-to-Treat population, by first using a generalized linear model with a log-link function to get an estimate of the logarithm of the rate ratio for mepolizumab vs. placebo and associated standard error. These estimates will then be combined with the global MEA115588 study using the pre-specified robust mixture prior to obtain the posterior distribution for the China rate ratio (on the log scale). A 95% posterior probability that the true rate ratio < 1 represents a high level of confidence for declaring a positive treatment benefit in Chinese patients in the context of a bridging study where substantial evidence of treatment benefit in global (non-Chinese) patients already exists.

Model Specification

- Generalized linear model assuming a negative binomial distribution
- Terms in the model:
 - Response:** number of recorded, on-treatment, clinically significant exacerbations experienced per subject.
 - Categorical:** treatment group, baseline maintenance OCS therapy (OCS vs. no OCS),
 - Continuous:** baseline disease severity (as % predicted FEV₁), number of exacerbations in previous year (as an ordinal variable)
 - Offset:** logarithm of time on treatment

Since this is a bridging study, to ensure comparability between results in MEA115588 and this study, the analysis model including the covariates are the same with MEA115588.

Model Results Presentation

- Treatment group model estimated exacerbation rates, the treatment rate ratio and associated SE and 95% CI will be presented.
- The pairwise treatment rate ratios and associated 95% CIs will also be presented graphically

Bayesian Dynamic Borrowing

A Bayesian dynamic borrowing model ([Schmidli](#), 2014) will be used to make inference about the logarithmic rate ratio of exacerbations in mepolizumab 100mg SC to Placebo in Chinese participants. The prior distribution will be a mixture with two components: the first component is based on the results from the MEA115588 study; the second component is a vague distribution centred on 0 representing 'no-effect'.

An initial (prior) weight of 50% is proposed for the informative global component of the robust mixture prior, with the remainder of the weight (50%) placed on the vague prior to reflect a conservative starting position regarding the assumed relevance of the global MEA115588 results to Chinese. Combining the two components and their respective weights gives the following 2-component mixture of normals:

$$p(\theta) = 0.5 * \text{Normal}(-0.7474, 0.1532) + 0.5 * \text{Normal}(0, 2.1256)$$

The prior mixture will be updated with the data from this study to obtain the posterior distribution. Assuming the standard error of the estimated logarithmic rate ratio in this study is known, the posterior distribution will also be a mixture of normal (see details below). The posterior weight given to the global MEA115588 study data is commensurate with the strength of evidence of similarity between the MEA115588 data and the China data. The BDB analysis [[Schmidli](#), 2014] 'learns' how much of the global MEA115588 study information to borrow based on the consistency between the observed rate ratio in the China and global studies and updates the weight on the global MEA115588 results accordingly.

The mean, median, 90% credible interval and 95% credible interval of this posterior distribution of the rate ratio will be reported, along with the probability that true rate ratio

Model Specification

is less than 1 (equivalent to the log rate ratio being less than 0). The mean and SE of log rate ratio will be presented as well.

The posterior distribution

The robust mixture prior was constructed as weighted average of global MEA115588 and weak priors, which followed the structure:

$$\text{Robust mixture} = w \times \text{Normal}(m_{global}, \sqrt{v_{global}}) + (1 - w) \times \text{Normal}(m_{vague}, \sqrt{v_{vague}})$$

Where $m_{global} = -0.7474$, $v_{global} = 0.1532^2$, $m_{vague} = 0$, $v_{vague} = 2.1256^2$ and $w = 0.5$.

Assumed the observed log rate ratio from this study has the distribution with mean m_{china} and variance v_{china} , which were the point estimate and squared standard error of the log rate ratio from negative binomial regression defined previously. The sampling distribution for the observed data will be combined with robust mixture prior using standard conjugate Bayesian theory to obtain a posterior mixture distribution:

$$\text{Posterior mixture} = w^* \times \text{Normal}\left(m_{global}^*, \sqrt{v_{global}^*}\right) + (1 - w^*) \times \text{Normal}(m_{vague}^*, \sqrt{v_{vague}^*})$$

where:

$$m_{global}^* = v_{global}^* \left(\frac{m_{global}}{v_{global}} + \frac{m_{china}}{v_{china}} \right) \text{ and } \frac{1}{v_{global}^*} = \frac{1}{v_{global}} + \frac{1}{v_{china}}$$

$$m_{vague}^* = v_{vague}^* \left(\frac{m_{vague}}{v_{vague}} + \frac{m_{china}}{v_{china}} \right) \text{ and } \frac{1}{v_{vague}^*} = \frac{1}{v_{vague}} + \frac{1}{v_{china}}$$

$$w^* = \frac{C_{global} \times w}{C_{global} \times w + C_{vague} \times (1 - w)}$$

$$C_{global} = \frac{\exp\{-0.5(m_{china} - m_{global})^2 / (v_{global} + v_{china})\}}{\sqrt{v_{global} + v_{china}}}$$

$$C_{vague} = \frac{\exp\{-0.5(m_{china} - m_{vague})^2 / (v_{vague} + v_{china})\}}{\sqrt{v_{vague} + v_{china}}}$$

The posterior means and variances of each component are obtained from conjugate Bayesian updating of that individual prior component, and the posterior weight is a function of the prior weight and coefficients C_{global} and C_{vague} (Schmidli, 2014)

Subgroup Analyses

Subgroup analyses of the primary endpoint will be carried out to assess consistency of the intervention effect across the following subgroups:

- Age group: <65, ≥ 65
- Sex: female vs male

Model Specification

- Weight: ≤ 60 kg, $> 60-\leq 75$ kg, > 75 kg
- Baseline predicted pre-bronchodilator FEV1: $\leq 60\%$, $> 60\%-80\%$, $> 80\%$
- number of exacerbations in the year prior to screening (i.e., 2, 3, 4+)
- Baseline use of maintenance oral corticosteroids
- Baseline airway reversibility: reversible or not reversible defined in Section 6.2.9.
- blood eosinophil count at screening: < 150 , $\geq 150-\leq 300$, $\geq 300-\leq 500$, ≥ 500 cells/ μ L
- Randomization stratification factor: < 300 , ≥ 300 cells/ μ L
- If the number of participants is too small (less than [10%]) within a subgroup, then the subgroup categories may be redefined prior to unblinding the study.

Missing data imputation

- The primary analysis using the negative binomial model assumes that missing data is missing at random (MAR).

4.2.2. Sensitivity analyses

- Ordinarily, an analysis under a MAR assumption is implemented using direct likelihood, by introducing an offset into the log-linear model to allow for the length of the observation period. Using an underlying negative binomial model, missing data post study withdrawal of treatment will be imputed conditional upon the subjects own observed number of events prior to withdrawal of treatment under MAR assumption. This approach involves firstly fitting the negative binomial generalised linear model to the data, and sampling from the posterior distribution (likelihood function multiplied by a non-informative prior) of the estimated parameters (i.e. the betas) associated with the independent variables. The number of exacerbations that would have been seen based on various assumptions is then estimated for subjects who withdraw of treatment early. This number is combined with the observed exacerbations and the data is analysed as for the primary endpoint [Keene, 2014]. This analysis is repeated multiple times and the results combined using Rubin's formulae [Barnard, 1999] as implemented in PROC MIANALYZE in SAS.
- Since this is a bridging study, to keep consistent analysis model, the stratification variable EOS level at screening (≥ 300 cells/ μ L vs. < 300 cells/ μ L) will be not included into the primary analysis. To test the impact of stratification variable for the model, further sensitivity analysis will be performed adding EOS level at screening (≥ 300 cells/ μ L vs. < 300 cells/ μ L) into the primary negative binomial model, the missing data is assumed as missing at random (MAR).

All the sensitivity analyses will not use BDB method to implement.

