4.2. Treatment Arms and Duration

Eligible subjects will be requested to participate for a maximum of 56 weeks (Visit 1 to Visit 15, inclusive) in the main study. A sub-set of subjects will participate in the PK sub-study for a total of 64 weeks (Visit 1 to Visit 15-2, inclusive). Subjects will remain on their existing standard of care asthma therapy whilst completing the three phases of the study, as described in [Table 4](#).

Subjects who meet the eligibility criteria will be randomized to receive either mepolizumab (100 mg) or placebo at a 1:1 ratio.

Subjects will be stratified based on blood eosinophil count at screening (≥ 300 cells/ μ L, < 300 cells/ μ L). A minimum of 150 subjects will be enrolled with blood eosinophil count ≥ 300 cells/ μ L.

Table 4 Study Phases

Phase	Phase Title	Duration	Description
1	Pre-screening	0-4 weeks	Details about the study and procedures will be explained through the informed consent process. The Pre-screening Visit (Visit 0) can occur on the same day as the Screening Visit (Visit 1) but must be completed prior to initiating any Visit 1 procedures.
2	Screening / Run-in	1 to 4 weeks	Subjects who meet all the eligibility criteria at Visit 1 (Screening), will enter the run-in period

Phase	Phase Title	Duration	Description
			for a minimum of 1 week and a maximum of 4 weeks in order to continue to assess the subject's eligibility for the study as well as to collect baseline eDiary data. Those subjects that are not eligible to continue in the study at the end of the 4-week run-in period will be deemed run-in failures (see Section 5.4).
3	Treatment	52 weeks	
At Visit 2 (Week 0) those subjects who successfully complete the run-in period as well as meet the pre-defined randomization criteria will be randomized; those subjects that do not meet the pre-defined randomization criteria will be deemed run-in failures (see Section 5.4). Study medication will be administered SC every 4 weeks for a total of 13 doses (Visit 2 to Visit 14, inclusive). The treatment period will conclude approximately 4 weeks after the subject was administered their last dose of double-blind study treatment.
 
PK samples will be collected at Week 0, 1, 2, 4, 24, and Week 48, 49, 50, 52, 56, 60 (or 0, 1, 2, 4, 8, 12 weeks after last dose) in subjects who provided consents for PK sub-study.

*For information on criteria relating to study treatment withdrawal, refer to Section [5.5](#)

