6.2. Study Treatment Assignment

At Visit 2 (Week 0) those subjects who meet the randomization eligibility criteria will be randomized in a 1:1 ratio (mepolizumab: placebo) to receive one of the following study treatments in addition to their baseline asthma treatment:

Mepolizumab 100 mg SC into the upper arm or thigh

Placebo 0.9% sodium chloride SC into the upper arm or thigh

Subjects will be stratified based on blood eosinophil count at screening (≥ 300 cells/ μL , < 300 cells/ μL). A minimum of 150 subjects will be enrolled with blood eosinophil count ≥ 300 cells/ μL .

Subjects eligible to enter the study will be assigned to treatment randomly via IWRS. In addition, IWRS will also be used to manage the entry of eligible subjects into the pharmacokinetic sub-study; subjects may not be permitted to enter the pharmacokinetic sub-study if the planned number of subjects in mepolizumab treatment arm has been reached.

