9.2. Sample Size Determination

9.2.1. Sample Size Assumptions

The sample size of 300 participants (considering 256 evaluable participants and additional 44 subjects for drop-out) in a 1:1 ratio has been determined by the superiority testing of mepolizumab 100 mg SC vs. placebo, there will be 90% power to detect a 40% decrease in the exacerbation rate from 1.7 per annum (p.a.) on placebo to 1.02 p.a. on mepolizumab 100mg SC using a two sided 5% significance level. The calculation assumes the number of exacerbations per year follows a negative binomial distribution [Keene, 2007] with a dispersion parameter $k=0.8$.

During the blinded evaluation, the clinically significant exacerbations which had occurred during the treatment period were analyzed using a generalized linear model assuming a negative binomial distribution and covariates of baseline maintenance OCS therapy (OCS vs. no OCS), EOS level at screening (≥ 300 cells/ μ L vs. < 300 cells/ μ L), number of exacerbations in previous year (as an ordinal variable) and baseline disease severity (as % predicted FEV1). The blinded evaluation estimated, the overall event rate based on an assessment of blinded data was observed as 0.78 p.a., the dispersion was 2.0. This was lower than the expected overall event rate of the original study design assumptions.

This observed reduction for overall events at blinded evaluation can be explained by a reduction in exacerbation events during the COVID-19 pandemic, which was not unique in China, it is still expected that the treatment effect of Mepolizumab compared with placebo will be the same in Chinese SEA population as the original study design assumption. Therefore, according the formula [Friede, 2010]

$$\bar{\lambda} = (\lambda_T + \lambda_P)/2$$

where $\bar{\lambda}$ is the observed overall events rate based on an assement of blinded data, the λ_T and λ_P are the event rates in the treatment and placebo groups, and assuming the reduction in exacerbation rate with Mepolizumab will remain 40% under pandemic, the estimated event rates λ_T and λ_P for Mepolizumab 100mg SC and placebo are 0.975 and 0.585 p.a. respectively. On the other hand, there exists a difference for the estimate of dispersion when data is blinded or unblinded, so that the blinded dispersion estimate is adjusted by the difference between blinded and unblinded, which is $1.6=2.0 * (0.796 / 0.972)$, where the dispersion in MEA115588 study were 0.796 (unblinded) vs. 0.972 (blinded).

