9.4.1.1. Primary Analyses

The primary treatment effect to be estimated in this study is the frequency of clinically significant exacerbations of asthma over the 52-week treatment period expressed as an exacerbation rate p.a. Exacerbations from the start of treatment until 4 weeks after the last dose of study drug will be used in the analysis. Exacerbations which are separated by less than 7 days will be treated as a continuation of the same exacerbation.

The numbers of clinically significant exacerbations are assumed to follow a negative binomial distribution. The logarithm of time on treatment will be used as an offset variable. The primary analysis of the rate of exacerbations will use a generalized linear model with a log-link function. This model will include covariates of treatment group, baseline maintenance OCS therapy (OCS vs. no OCS), number of exacerbations in previous year (as an ordinal variable), baseline disease severity (as % predicted FEV1). The estimate of the logarithm of the rate ratio for mepolizumab vs. placebo and associated standard error will be the data used to update the robust mixture prior to obtain the final posterior distribution for the China rate ratio (on the log scale).

The mean, median and 90% credible interval of this posterior distribution of the rate ratio will be reported, along with the probability that true rate ratio is less than 1 (equivalent to the log rate ratio being less than 0).

The following 2-component mixture prior will be used for the log rate ratio:

$$p(\theta) = 0.5 * Normal(-0.7474, 0.1532) + 0.5 * Normal(0, 2.1256)$$

Sensitivity analysis will be conducted to assess the impact of different prior weights on the ‘informative’ component of the robust mixture prior, and the details will be specified in the RAP.

For the intercurrent event of withdrawal from study treatment, hypothetical strategy will be applied for primary analysis, where the logarithm of time on treatment will be used as an offset variable in the model.

The detailed missing data imputation method and supportive analysis will be defined in full RAP.

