4.3.2. Main analytical approach

Time to first clinically significant exacerbations

Endpoint / Variables

 • Time to first clinically significant exacerbations
Model Specification

 • Cox's proportional hazards model • Terms in the model:

Endpoint / Variables

 Response: time to first on-treatment, clinically significant exacerbation Categorical: treatment group, baseline maintenance oral corticosteroids (OCS vs no OCS) Continuous: baseline disease severity (as % predicted FEV1), number of exacerbations in the year prior to the study (as an ordinal variable (2, 3, 4+))
Model Checking & Diagnostics

 The proportional hazards assumption will be examined by obtaining the Kaplan-Meier estimates of the survival function $S(t)$ over time separately for each treatment group. In addition, the $\ln \{-\ln[S(t)]\}$ plot will be produced.
Model Results Presentation

 Hazard ratios and the percent reduction in risk of a first exacerbation at any time on-treatment during the study for the pairwise treatment comparisons with associated 95% CIs and p-values will be presented. The probability of having an on-treatment clinically significant exacerbation at week 16, 32 and 52 and 95% CI for each treatment group will be presented.
Sensitivity and Supportive Analyses

 As a supportive analysis, the analysis will be repeated using the “Per-protocol” analysis population.
Additional estimands

A supplementary analysis will be performed using the “treatment policy” strategy for the intercurrent event of discontinuation of treatment. This analysis will include both on-treatment and off-treatment clinically significant exacerbation data from subjects who withdraw from treatment prior to W52. Exacerbations will be included provided the exacerbation onset date is before week 52. Participants that have not experienced a clinically significant exacerbation on or before the end of study date/early withdrawal/lost to follow up study/ date of death day are censored at the end of study date/early withdrawal/date of death.

SGRQ at Week 52

Endpoint / Variables

 Mean change in St. Georges Respiratory Questionnaire at Week 52 
Details for how to score the SGRQ are outlined in the SGRQ manual (Mar, 2016).

Model Specification

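### The primary and all key secondary models omit the eosinophil stratum used in randomisation, and the 95% posterior criterion is never assessed with it; the likely loss is small and conservative

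*SAP*

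**What the plan says.** - **Design.** Protocol 6.2: "Subjects will be stratified based on blood eosinophil count at screening", cut at 300 cells/µL. SAP 1.2 agrees: "Randomization to study treatment will be stratified by blood eosinophil count at screening". Protocol 4.2 sets a floor for the upper stratum: "A minimum of 150 subjects will be enrolled with blood eosinophil count" at or above 300, which is half of the 300 randomised.
- **Primary model.** Protocol 9.4.1.1: "This model will include covariates of treatment group, baseline maintenance OCS therapy (OCS vs. no OCS), number of exacerbations in previous year", plus % predicted FEV1. SAP 4.2.1 lists the same terms. Neither includes eosinophils.
- **Key secondary models.** The Cox model in SAP 4.3.2 has "Categorical: treatment group, baseline maintenance oral corticosteroids (OCS vs no OCS"), plus % predicted FEV1 and prior exacerbations. The SGRQ and pre-bronchodilator FEV1 MMRMs also lack the stratum. The two hospitalisation/ED rate models follow the primary method.
- **Reason given.** SAP 4.2.2: "Since this is a bridging study, to keep consistent analysis model, the stratification variable EOS level at screening" is kept out of the primary analysis. SAP 4.2.1 says that the covariates match those of MEA115588.
- **What is planned with the stratum.** SAP 4.2.2 adds it to the primary negative binomial model as a sensitivity analysis, and states that no sensitivity analysis uses the borrowing method. SAP 4.2.1 also has subgroup analyses by stratum and by finer eosinophil bands.
- **Planning.** The blinded evaluation that gave rate 0.78 and dispersion 2.0 used "covariates of baseline maintenance OCS therapy (OCS vs. no OCS), EOS level at screening", among other terms (Protocol 9.2.1).

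**The concern.** A factor used to stratify randomisation normally belongs in the analysis model. If it predicts the outcome, leaving it out puts between-stratum variation into the dispersion. The model then reports a standard error larger than the stratified design warrants. Here that standard error, with the log rate ratio, is the whole China input to the Bayesian update.

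Three consequences follow:

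1. Some precision may be given up for a reason that does not require it.
2. The 66% stand-alone power, 88.6% success probability and 0.776 boundary rest on a dispersion from a covariate set that the primary model does not use.
3. A reader cannot learn from the planned outputs whether the 95% posterior criterion would be met with the stratum in the model. For the key secondary endpoints there is no eosinophil-adjusted estimate at all.

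**Working it through.** **Inputs from the documents.** 128 evaluable per arm ("considering 256 evaluable participants and additional 44 subjects for drop-out", Protocol 9.2.1); rates 0.975 and 0.585 p.a.; dispersion k = 1.6; prior 0.5·N(−0.7474, SD 0.1532) + 0.5·N(0, SD 2.1256); success if P(RR<1) ≥ 0.95.

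**Assumed, because the documents do not give them.** The rate ratio R between the ≥300 and <300 strata (1.0 to 3.0), and the share p in the ≥300 stratum (50% to 80%; the protocol fixes only the 50% floor).

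**Step 1: reproduce the plan.** Var(log RR) = (1/n)(1/λP + 1/λT + 2k) = (1.0256 + 1.7094 + 3.2)/128 = 0.04637, so SE = 0.2153. Power = Φ(0.5108/0.2153 − 1.96) = 66.0% (stated 66%). Applying the SAP 4.2.1 mixture update and integrating over the sampling distribution gives success 88.4% (stated 88.6%), false positive rate 11.7% (stated 11.8%) and boundary 0.776 to 0.777 (stated 0.776).

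**Step 2: omit a prognostic stratum.** Let c² be the squared coefficient of variation of the stratum rates. The model without the stratum sees dispersion k(1 + c²) + c². The adjusted SE comes from summing information over strata.

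Example, R = 2, p = 50%:
- Mean relative rate is 1.5 and c² = 2.5/2.25 − 1 = 0.111.
- Dispersion without the stratum is 1.6 × 1.111 + 0.111 = 1.889.
- SE without the stratum is √[(2.7350 + 3.7778)/128] = 0.2256.
- Adjusted information is 64/(2.7350/1.3333 + 3.2) + 64/(2.7350/0.6667 + 3.2) = 12.19 + 8.76 = 20.95, so SE = 0.2185.
- The ratio of unrounded SEs is 1.0325.
- Under stratified randomisation the true sampling SE of the unadjusted estimate is √[(2.7350 + 3.2 × 1.111)/128] = 0.2217. The reported 0.2256 therefore overstates even that estimator's own variability.

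Results with p = 50% and 1.6 taken as the stratum-adjusted dispersion, which is how the blinded evaluation obtained it:

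| R | SE adjusted | SE omitted | SE increase | Stand-alone power, adjusted / omitted | Success with borrowing, adjusted / omitted |
|---|---|---|---|---|---|
| 1.0 | 0.2153 | 0.2153 | 0% | 66.0 / 66.0% | 88.4 / 88.4% |
| 1.25 | 0.2157 | 0.2165 | 0.4% | 65.9 / 65.6% | 88.4 / 88.3% |
| 1.5 | 0.2164 | 0.2191 | 1.2% | 65.6 / 64.6% | 88.3 / 88.0% |
| 2.0 | 0.2185 | 0.2256 | 3.3% | 64.7 / 62.2% | 88.0 / 87.4% |
| 3.0 | 0.2229 | 0.2377 | 6.7% | 63.0 / 57.7% | 87.3 / 86.1% |

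With 80% in the ≥300 stratum the SE increase is only 0.2% to 2.4% for R from 1.25 to 3.0. Taking 1.6 instead as the dispersion without the stratum gives nearly the same SE increases (0.2% to 6.5% over all shares). The false positive rate with borrowing differs between the two models by about 0.2 points or less.

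**Step 3: does adding the stratum change the target?** With a log link, randomised treatment and no treatment-by-eosinophil interaction, the rate ratio is collapsible, so both models estimate the same log rate ratio. In simulated trials (128 per arm, equal strata, dispersion without the stratum set to 1.6, 3,000 trials per scenario) the mean log rate ratio with and without the term agreed within about 0.001. Mean differences in the SGRQ and FEV1 MMRMs behave in the same way. Hazard and odds ratios do not.

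**The case against.** The omission is open, reasoned and partly covered. Amendment 4 removed the term deliberately, and the SAP states why. Keeping the China model the same as the model behind the prior is a legitimate aim. The MEA115588 model cannot be inspected from these documents, and neither can the absence of a treatment-by-eosinophil interaction. The primary endpoint already has a pre-specified analysis with the stratum. The key secondary endpoints carry no multiplicity-controlled claim.

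The loss may also be smaller than the table shows. Maintenance OCS, prior exacerbations and % predicted FEV1 are in the model and may absorb part of any eosinophil effect, and the calculation leaves them out. The upper stratum may be well above half. The planning dispersion is itself approximate: 2.0 × 0.796/0.972 = 1.638, rounded to 1.6, which alone moves power from 65.4% to 66.0%.

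Most of this stands, and it limits the size of the point. It does not remove two gaps: the adjusted estimate never reaches the posterior criterion, and the key secondary endpoints have no adjusted analysis. Nor does matching the prior explain the omission from the MMRMs. The numerical prior covers only the primary endpoint. For SGRQ the SAP already makes an MMRM the main analysis and keeps an ANCOVA as the comparison with MEA115588.

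A reader might infer that the comparability reason is invalid throughout. It is not: for the Cox, logistic and proportional-odds models a further covariate changes the quantity estimated, so a matched model has real value there. A reader might also infer that the SAP 4.1.1 rule on wrongly stratified subjects has nothing to act on. It applies to the sensitivity and subgroup analyses.

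**Conclusion.** The point holds as a modest improvement to the analysis. The stratum is missing from the primary and all key secondary models, and matching MEA115588 does not require this for the rate ratios or the two MMRM mean differences, given no treatment-by-eosinophil interaction.

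The direction is conservative for the reported standard error. At equal strata the excess is 0% if eosinophils are not prognostic, about 1% at R = 1.5, about 3% at 2.0 and up to about 7% at 3.0, and less if the ≥300 stratum is well above 50%. Success with borrowing falls by at most 0.6 points for R up to 2 and by 1.2 points at 3. R is an assumption throughout.

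The documents do not support a stronger reading that the trial loses material power or that false positives rise. The firmer findings do not depend on R: the planning figures come from a different covariate set, and no planned output shows the 95% criterion with the stratum included.

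**What to change.** Before unblinding:

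- Add the actual screening eosinophil stratum (<300, ≥300) as a categorical term to the primary and secondary negative binomial models and to the SGRQ and FEV1 MMRMs.
- Keep the model without it, also run through the mixture prior, as the MEA115588-comparability sensitivity analysis.
- For the Cox, logistic and proportional-odds models, report eosinophil-adjusted results beside the matched model.
- At minimum, pass the already planned eosinophil-adjusted primary estimate through the mixture prior and report its posterior probability that the rate ratio is below 1.

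The cost is a wording change in the protocol and SAP and a few extra model runs. The covariate is already collected and already specified for the sensitivity analysis. The small downside is one term of difference between the main China model and the MEA115588 model.
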